8.1 Eligibility for registration

All patients must be registered before start of treatment and must meet all of the following eligibility criteria, which will be checked at registration.

8.1.1 Inclusion criteria

- ◆ Documented relapsed/refractory CLL or SLL requiring treatment according to IWCLL criteria (no limits on previous treatment lines; CD20 and steroids are not considered prior therapy lines).
- ◆ Age at least 18 years.
- ◆ Adequate bone marrow function defined as:
 - Absolute neutrophil count (ANC) $>0.75 \times 10^9/L$
 - Platelet count $>30,000 /\mu L$ $30 \times 10^9/L$.
 - Hemoglobin $>8.0 \text{ g/dL}$ (5 mmol/L)Unless directly attributable to CLL infiltration of the bone marrow, proven by bone marrow biopsy
- ◆ Creatinine clearance (CrCL) $\geq 30 \text{ ml/min}$ calculated according to the modified formula of Cockcroft and Gault or directly measured with 24hr urine collection.
- ◆ Adequate liver function as indicated
 - Serum aspartate transaminase (AST) or alanine transaminase (ALT) $\leq 3.0 \times$ upper limit of normal (ULN)
 - Bilirubin $\leq 1.5 \times$ ULN (unless bilirubin rise is due to Gilbert's syndrome or of non-hepatic origin)
 - Prothrombin time (PT)/International normal ratio (INR) $<1.5 \times$ ULN and PTT (activated partial thromboplastin time [aPTT]) $<1.5 \times$ ULN (unless abnormalities are related to coagulopathy or bleeding disorder).
- ◆ Negative serological testing for hepatitis B (HBsAg negative and anti-HBc negative; patients positive for anti-HBc may be included if PCR for HBV DNA is negative and HBV-DNA PCR is performed every month until 12 months after last dose), negative testing for hepatitis C RNA within 42 days prior to registration.
- ◆ WHO/ECOG performance status 0-3 (appendix C), stage 3 only if attributable to CLL.
- ◆ Negative pregnancy test at study entry (for women of childbearing potential).
- ◆ Male and female subjects of reproductive potential must agree to use both a highly effective method of birth control (e.g. implants, injectables, combined oral contraceptives, some

intrauterine devices [IUDs], complete abstinence , or sterilized partner) and a barrier method (e.g., condoms, cervical ring, sponge, etc.) during the period of therapy and for 90 days after the last dose of study drug.

- ◆ Ability and willingness to provide written informed consent and to adhere to the study visit schedule and other protocol requirements.
- ◆ Written informed consent.

8.1.2 Exclusion criteria

- ◆ Any prior therapy with ibrutinib and/or venetoclax.
- ◆ Transformation of CLL (Richter's transformation).
- ◆ Patients with a history of confirmed progressive multifocal leukoencephalopathy (PML).
- ◆ Malignancies other than CLL currently requiring systemic therapies or not being treated in curative intention before or showing signs of progression after curative treatment.
- ◆ Known allergy to xanthine oxidase inhibitors and/or rasburicase if no other appropriate prevention of tumorlysis is considered feasible by the treating physician.
- ◆ Known bleeding disorders (e.g., von Willebrand's disease or hemophilia).
- ◆ Uncontrolled or active infection.
- ◆ Patients requiring treatment with a strong cytochrome P450 (CYP) 3A inhibitor (see appendix K). or anticoagulant therapy with warfarin or phenprocoumon or other vitamin K antagonists.

Please note: Patients being treated with NOACs can be included, but must be properly informed about the potential risk of bleeding under treatment with ibrutinib.

- ◆ History of stroke or intracranial hemorrhage within 6 months prior to registration.
- ◆ Major surgery within 28 days prior to registration.
- ◆ Use of investigational agents which might interfere with the study drug within 28 days prior to registration.
- ◆ Vaccination with live vaccines within 28 days prior to registration
- ◆ Steroid therapy within 7 days prior to registration, with the exception of inhaled steroids for asthma, topical steroids, steroids up to 25 mg of prednisolone daily to control autoimmune phenomenon's, or replacement/stress corticosteroids.
- ◆ Pregnant women and nursing mothers.
- ◆ Any psychological, familial, sociological and geographical condition potentially hampering compliance with the study protocol and follow-up schedule.

8.2 Eligibility for randomization

- ◆ MRD negative peripheral blood after cycle 12.

- ◆ MRD negative peripheral blood and bone marrow at day 15 of cycle 15.
- ◆ At least SD after cycle 15.

8.3 Eligibility for Ibrutinib monotherapy in MRD-positive patients

- ◆ MRD positive peripheral blood after cycle 12 and/or MRD positive peripheral blood and/or bone marrow at day 15 of cycle 15.
- ◆ At least SD after cycle 15

9 Treatment

9.1 Treatment with ibrutinib and venetoclax

All patients should start protocol treatment (cycle 1, day 1), within 28 days after registration, or in case of new uncontrolled infection occurring after registration, when infection is under control.

All patients receive 15 cycles of ibrutinib + venetoclax (with ramp up and delayed start, see below). Each cycle has a duration of 28 days.

After 15 cycles of ibrutinib + venetoclax, subsequent treatment will be based on MRD status:

- Patients not achieving MRD negativity after cycle 12 (PB) AND/OR at day 15 of cycle 15 (PB+BM) continue on ibrutinib maintenance (non-randomized patients)
- Patients achieving MRD negativity after cycle 12 (PB) AND at day 15 of cycle 15 (PB+BM) are randomized 1:2 between ibrutinib maintenance (Arm A) and stopping treatment (observation) (Arm B).

Ibrutinib will be administered as a daily oral dosage of 420 mg (3 x 140 mg) starting on day 1 of cycle 1.

Venetoclax administration starts in cycle 3. Assessment of subject-specific factors for level of risk of TLS and providing prophylactic hydration and anti-hyperuricemics to subjects prior to first dose of venetoclax to reduce risk of TLS is mandatory (see appendix G). Venetoclax will be administered orally once daily beginning with a dose ramp-up period. The initial venetoclax dose is 20 mg. After one week of treatment at 20 mg, the dose will be escalated to 50 mg, followed by subsequent increases, each after one week, to 100 mg, 200 mg and the maximum dose of 400 mg. The 5-week ramp-up dosing schedule is designed to gradually reduce tumor burden (debulk) and decrease the risk of TLS.

Patients with a high tumor burden or assessed as high risk for TLS at baseline, should be re-assessed for TLS risk, at the end of cycle 2 (before venetoclax ramp up) including a CT-scan,

absolute leucocyte count (ALC) and creatinine clearance (CrCl, directly measured with 24hr urine collection or calculated according to the modified formula of Cockcroft and Gault, appendix E).

For patients with CrCL between 30-50 ml/min , inclusion in the trial is acceptable if:

- ◆ CrCl and ALC count will be re-assessed at end of cycle 2 (before venetoclax ramp up)
- ◆ Upon significant (above 15%) creatinine increase, treatment will be put on hold for a work up by a nephrologist to assess whether treatment can be reinitiated
- ◆ Re-assessment with a CT scan will be performed at end of cycle 2
(using contrast is up to local investigator based on kidney function)
- ◆ Re-assessment of comorbidities will be performed at end of cycle 2

Please note: patients with a CrCl between 30 ml/min and 50 ml/min are considered as patients at greater risk for TLS and must be hospitalized during ramp-up independently of their disease burden.

In order to correctly diagnose a laboratory or clinical TLS at an early stage certain safety measures must be followed (see appendix G) for further information.

Patients will continue treatment until suspected progressive disease according to IWCLL after start of cycle 6. In case of suspected progression, this needs to be confirmed by CT and bone marrow biopsy. Patients with at least stable disease (SD) will continue on trial; patients with progressive disease will go off protocol treatment

In the case of signs of progression *before* start of cycle 6 i.e. Richter's, progression needs to be confirmed by CT and bone marrow biopsy. If progression is proven after at least 2 cycles of venetoclax the patient should go off protocol.

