- Hemoglobin A_{1c} (for diabetic patients)

From: Miller MD, Paradi

Miller MD1, Paradis CF, et al Rating chronic medical illness burden in geropsychiatric practice and research: application of the Cumulative Illness Rating Scale. Psychiatry Res. 1992 Mar;41(3):237-48.

G. Tumor Lysis prophylaxis

Risk categories for development of tumor lysis syndrome (TLS)

Based on review of all currently available data, three risk categories for developing TLS were defined including the size of the enlarged lymph nodes and the absolute lymphocyte count (ALC). In addition, the creatinine-clearance (CrCl) of the patient needs to be taken into account by the investigator (see below).

The following risk categories were defined:

	Low Risk	Medium Risk	High Risk	
Lymph Nodes	All measurable lymph nodes with the largest diameter <5 cm by radiographic assessment	Presence of any single measurable lymph node with the largest diameter ≥5 cm and <10 cm by radiologic assessment	A single measurable lymph node with the largest diameter ≥5 cm by radiologic assessment.	Any single measurable lymph node with the largest diameter ≥10 cm by radiologic assessment
	AND	OR	AND	
Absolute lymphocyte Count (ALC)	< 25 × 10 ⁹ /L	≥ 25 × 10 ⁹ /L	≥ 25 × 10 ⁹ /L	

All patients enrolled in the trial will be assessed at screening and categorized based on their tumor burden, as described above. A repetition of imaging for evaluation of lymph node size before the administration of the first dosage of venetoclax is required for patients with high risk or CrCL 30-50ml/min. Patients can be restaged into a lower TLS risk group at any time according to their ALC or repetition of imaging. Imaging is due to the investigator's discretion; ultrasound may be accepted in case of clear results.

Please note: Patients with **CrCl < 80 ml/min** should be monitored very closely for signs of TLS, especially if they are in the intermediate or high risk TLS risk category (lymph node ≥ 5 and/or ALC ≥ 25× 10⁹/L).

Patients with **CrCl 30-50 ml/min** should be handled as high risk patients.

Initial dosing and monitoring**Low and medium risk patients -**

- Administration of an oral uric acid reducer (such as allopurinol 300 mg/day) beginning at least 72 hours prior to first dose and continued until at least 28 days after last dose escalation.

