- Any patient who, at any dose, develops clinically significant electrolyte abnormalities must have his or her subsequent venetoclax dose withheld until the electrolyte abnormalities resolve.

- Patients who develop electrolyte abnormalities should undergo aggressive management and further monitoring as outlined below (see under 'further actions').
- Oral hydration consisting of fluid intake of >2 L/day should be maintained during the whole ramp-up period of venetoclax.

The following table summarizes the safety precautions for mitigation of TLS depending on different risk categories:

Recommended TLS Prophylaxis Based on Tumor Burden from Clinical Trial Data (consider all patient co-morbidities before final determination of prophylaxis and monitoring schedule)

Tumor Burden		Prophylaxis		Blood Chemistry Monitoring ^{c,d}
		Hydration ^a	Anti-hyperuricemics	Setting and Frequency of Assessments
Low	All LN <5 cm AND ALC <25 x10 ⁹ /L	Oral (1.5-2 L)	Allopurinol ^b	Outpatient 1. Pre-dose, 6 to 8 hours, 24 hours at first dose of 20 mg and 50 mg 2. Pre-dose and 24 hours at subsequent ramp-up doses
Medium	Any LN 5 cm to <10 cm OR ALC ≥25 x10 ⁹ /L	Oral (1.5-2 L) and consider additional intravenous	Allopurinol	Outpatient 3. Pre-dose, 6 to 8 hours, 24 hours at first dose of 20 mg and 50 mg 4. Pre-dose and 24 hours at subsequent ramp-up doses 5. Consider hospitalization for subjects with CrCl <80mL/min at first dose of 20 mg and 50 mg; see below for monitoring in hospital
High	Any LN ≥10 cm OR ALC ≥25 x10 ⁹ /L AND any LN ≥5 cm	Oral (1.5-2 L) and intravenous (150-200 mL/hr as tolerated)	Allopurinol; rasburicase is recommended if baseline uric acid is elevated (ALLOPURINOL SHOULD NOT BE GIVEN AT SAME DAY AS RASBURICASE)	In hospital (recommended) at first dose of 20 mg and 50 mg 6. Pre-dose, 6 to 8, and 24 hours Outpatient at subsequent ramp-up doses 7. Pre-dose, 6 to 8 hours, 24 hours

ALC = absolute lymphocyte count; LN = lymph node.

- Administer intravenous hydration for any patient who cannot tolerate oral hydration.
- Start allopurinol or xanthine oxidase inhibitor 2 to 3 days prior to initiation of venetoclax.
- Evaluate blood chemistries (potassium, uric acid, phosphorus, calcium, and creatinine); review in real time.
- For subjects at low/medium risk of TLS, monitor blood chemistries pre-dose and 24 hours at each subsequent ramp-up dose. For subjects at high risk of TLS, monitor blood chemistries pre-dose, at 6-8 hours and at 24 hours at each dose level.

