Hydration: Ensure adequate hydration prior to initiating therapy with venetoclax and throughout the ramp-up phase, especially the first day of each ramp-up dose. Administer intravenous (IV) fluids as indicated based on overall risk of TLS or for those who cannot maintain adequate oral hydration.

Anti-hyperuricemic agents: Administer uric acid reducing agents (e.g., allopurinol). Start 2-3 days prior to initiation of venetoclax; consider continuing through the ramp-up phase.

Laboratory Assessments:***Pre-dose (within 24 hours prior to ramp-up dose) :***

- Sodium, potassium, calcium, phosphate, chloride
- uric acid, urea, total bilirubin, serum creatinine
- LDH
- complete blood count (CBC), including hemoglobin, platelets and white blood cell count with differentials
- liver enzymes (AST, ALT, alkaline phosphatase)

Assess blood chemistries mentioned above prior to initiating venetoclax to evaluate kidney function and correct pre-existing hyperuricemia, hyperkalemia, hyperphosphatemia, or hypocalcemia to normal levels. Reassess blood chemistries before starting each subsequent ramp-up dose of venetoclax.

Post-dose: For subjects at low or medium risk of TLS, monitor blood chemistries at 6-8 hours and at 24 hours after initiating venetoclax at the 20 mg and 50 mg doses. For subjects at high risk of TLS, monitor blood chemistries in the hospital at 4, 8, 12 and 24 hours after initiating venetoclax at the 20 mg and 50 mg doses; subsequent ramp-up doses can be administered in the outpatient setting with monitoring of blood chemistries at 6-8 hours and at 24 hours after initiating venetoclax. Electrolyte abnormalities should be corrected promptly. The next dose of venetoclax should not be administered until the 24 hour blood chemistry results have been evaluated.

Hospitalization:

Based on physician assessment, some patients, especially those at greater risk of TLS and patients with CrCl 30-50 ml/min, may require hospitalisation on the day of the first dose of venetoclax for more intensive prophylaxis and monitoring during the first 24 hours. Hospitalisation should be considered for subsequent dose increases based on reassessment of risk.

Scoring of tumor lysis syndrome and further actions

The below listed criteria defined by Cairo and Bishop should be used to diagnose a laboratory or clinical TLS.

Laboratory Tumor Lysis Syndrome (LTLS):

Laboratory Parameter	Laboratory Result
Uric Acid	≥ 476 μmol/L (≥ 8.0 mg/dL) or 25% increase from baseline

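### Section 9.1 and Appendix G give conflicting tumor lysis precautions for patients with creatinine clearance 30-50 ml/min and for high-risk patients, chiefly on hospitalization and blood sampling

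*Protocol*

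**What the plan says.** **Hospitalization, CrCl 30-50 ml/min.** Section 9.1 treats these patients as being at raised risk of tumor lysis syndrome (TLS) and says they "must be hospitalized during ramp-up independently of their disease burden". It then refers to Appendix G for the safety measures. Appendix G says that they "should be handled as high risk patients". The high-risk row of its prophylaxis table reads "In hospital (recommended) at first dose of 20 mg and 50 mg" and then "Outpatient at subsequent ramp-up doses". Its later hospitalization paragraph makes admission depend on the physician's assessment, for a subset described as follows: "especially those at greater risk of TLS and patients with CrCl 30-50 ml/min, may require hospitalisation on the day of the first dose".

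**Blood sampling, high risk.** The high-risk bullets in Appendix G require samples before the dose and at 6-8 and 24 hours after it, at every dose level. The table agrees, and so does its footnote: "For subjects at high risk of TLS, monitor blood chemistries pre-dose, at 6-8 hours and at 24 hours at each dose level". The post-dose paragraph instead says to "monitor blood chemistries in the hospital at 4, 8, 12 and 24 hours after initiating venetoclax at the 20 mg and 50 mg doses", with 6-8 and 24 hours at the later steps.

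**Hydration.** The high-risk bullets say: "Oral hydration consisting of fluid intake of >2 L/day should be maintained during the whole ramp-up period of venetoclax". They name no routine intravenous fluid. The table gives 1.5-2 L by mouth in every risk group and, for high risk, adds intravenous fluid at 150-200 mL/hr as tolerated.

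**Uric acid reducer.** The bullets start it 72 hours or more before the first dose and continue it for at least 28 days beyond the last escalation. A table footnote and the paragraph on anti-hyperuricemic agents start it two to three days before. That paragraph asks only that continuation through ramp-up be considered.

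**Use of the TLS data.** Section 12.3.1 makes every TLS case a serious adverse event. Under section 14.4.4, interim analyses IA (first 15 patients) and IB (first 10 patients with CrCl 30-50) take place after cycle 3, and both report TLS.

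**The concern.** Section 9.2.1 describes TLS as severe and potentially fatal, and section 9.1 makes prophylaxis mandatory by reference to Appendix G. For the renal group that the protocol itself singles out, a site finds admission stated as an obligation in one place, a recommendation at two doses in another, and an option on one day in a third. A site that works from Appendix G alone could treat such a patient as an outpatient without noticing that section 9.1 requires otherwise.

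There is also a measurement side. Appendix G defines laboratory TLS by at least two abnormal serum values, so a case is recorded only if blood is drawn while the values are abnormal. If sites use different sampling schedules, the TLS counts in IA and IB pool patients observed with different intensity.

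**Working it through.** There is no stated figure to reproduce. The check is a comparison of texts, a count of draws, and one illustration.

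**1. Hospitalization for CrCl 30-50, by strength and duration**

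| Place | Strength | When |
|---|---|---|
| Section 9.1 | mandatory | during ramp-up |
| Appendix G, high-risk table row | recommended | first 20 mg and 50 mg doses; outpatient afterwards |
| Appendix G, hospitalization paragraph | possible, by physician assessment | day of first dose; to be considered at later increases |

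The sentence that assigns CrCl 30-50 to high risk makes the table row apply to the same patients as section 9.1. No sentence gives an order of precedence.

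**2. Scheduled post-dose draws for a high-risk or CrCl 30-50 patient.** The five dose levels are 20, 50, 100, 200 and 400 mg (section 9.1.1).

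- Bullets, table and footnote: 2 draws (6-8 h, 24 h) × 5 levels = 10.
- Post-dose paragraph: 4 draws (4, 8, 12, 24 h) × 2 levels + 2 draws × 3 levels = 8 + 6 = 14.
- At 20 mg and 50 mg together: 2 × 2 = 4 against 4 × 2 = 8, a ratio of 2. Over the whole ramp-up: 14 / 10 = 1.4.

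**3. Who meets the sampling conflict.** For low and medium risk the times agree across bullets, table and post-dose paragraph. Patients at high risk at baseline are reassessed at the end of cycle 2 (section 9.1), and Appendix G allows restaging to a lower group. The conflict therefore reaches patients who are high risk or CrCl 30-50 when ramp-up begins. That covers the IB patients by definition, but only the corresponding members of IA.

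**4. Lesser conflicts**

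- Oral volume: more than 2 L/day and 1.5-2 L do not overlap. For high-risk patients the table also has an intravenous component that the high-risk bullets lack.
- Uric acid reducer, start: 72 hours is 3 days, so a 3-day start satisfies both texts and only a 2-day start breaks one of them.
- Uric acid reducer, duration: a minimum of 28 days after the last escalation differs from an invitation to consider continuing through ramp-up.

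**5. Illustration for IB.** The documents give neither a TLS rate nor a detection probability, so both are assumed here. With true rate p and detection probability s, the chance that 10 patients show at least one case is 1 − (1 − p·s)^10.

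| p | s = 1 | s = 0.75 | s = 0.5 |
|---|---|---|---|
| 0.05 | 0.40 | 0.32 | 0.22 |
| 0.10 | 0.65 | 0.54 | 0.40 |
| 0.20 | 0.89 | 0.80 | 0.65 |

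This shows that a 10-patient look is sensitive to detection. It does not estimate how far detection differs between the two schedules.

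**The case against.** **The appendix wording does not release a site from section 9.1.** A reader might infer that a site could leave a CrCl 30-50 patient at home and still comply with the protocol. The documents do not support that: section 9.1 is unconditional, and such a site would breach it. The table is also headed as recommended prophylaxis and tells the physician to weigh comorbidities. What stands is that section 9.1 sends readers to an appendix that names the same group and states a weaker rule.

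**The sampling schedules are nested.** Draws at 8 and 24 hours meet the 6-8 and 24 hour rule, so the denser schedule satisfies both texts. That is true, but the sparser one omits the 4 and 12 hour draws that the post-dose paragraph asks for.

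**Draws are not detections.** A reader might infer a two-fold difference in TLS detection. The factor of 2 counts draws at two of the five steps; overall it is 1.4. Section 9.7.1 places the earliest chemistry changes at 6 to 8 hours after a dose, so on the protocol's own account the 4-hour draw precedes that window. Every version keeps the 24-hour sample. This objection stands.

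**Hydration.** A reader might infer that the table prescribes less fluid for high-risk patients. With its intravenous part included, it does not show that. The valid points are the different oral volumes and the intravenous fluid missing from the high-risk bullets.

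**The interim analyses are descriptive.** Section 14.4.4 marks IA and IB as safety only and gives no TLS threshold. A reader might infer that the conflict invalidates them or reaches the efficacy result. Neither follows.

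**Conclusion.** The contradictions are in the current protocol text and must be resolved. The most serious is hospitalization for CrCl 30-50 ml/min, where three statements differ in strength and duration. Next is high-risk sampling, with 2 against 4 post-dose draws at each of the 20 mg and 50 mg steps and 10 against 14 overall. Hydration and the duration of the uric acid reducer are lesser conflicts; its start times conflict only for a 2-day start.

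The case for correction rests on patient safety: a group that the protocol itself regards as vulnerable has no single stated rule for a potentially fatal complication. Uneven TLS ascertainment in IB, and in the high-risk or CrCl 30-50 members of IA, is a reasonable secondary inference. It assumes that sites would actually follow different texts, and its size cannot be computed from the documents. The primary endpoint, alpha and sample size are unaffected.

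**What to change.** Reconcile section 9.1 with all parts of Appendix G that bear on this: the sentence on CrCl 30-50, the risk-group bullets, the prophylaxis table and its footnotes, and the anti-hyperuricemic, post-dose and hospitalization paragraphs. Give one rule per risk group for setting, sampling times, hydration and uric acid reducer. State it once and cross-reference it elsewhere, including from section 9.4, where reinitiation in arm B uses the same TLS precautions through section 9.2.1.

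State which sampling schedule underlies the TLS counts in IA and IB. If patients have already been treated under differing schedules, report which one each patient followed.

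Which rule is right is for the sponsor's clinicians; this review takes no view. The cost is a protocol amendment and a letter to sites, with no change to sample size or to the primary analysis.
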